- Outpatient irradiation and baseline MED testing for Irradiation Condition 1 and Irradiation Condition 2 will occur on Day -2. Two areas of the back will be defined for irradiation, followed by MED assessments at 10 ±2 minutes, 1 hour ±5 minutes (Day -2) and at 24 hours ±10 minutes (Day -1) post irradiation.
- Baseline irradiation for Irradiation Condition 3 will occur on Day -1 with baseline inflammatory responses assessed at 10 ± 2 minutes, 1-hour ± 5 minutes (Day -1) and at 24 hours ± 10 minutes (Day 1) post Day -1 irradiation.
- 8 Preliminary MED irradiation will be performed on Day -3 with confirming evaluation on Day -2.
- 9 Planned time relative to the drug administration
- samples should be taken before drug administration

c27983101-03 Clinical Trial Protocol

Page 8 of 79

Proprietary confidential information © 2020 Boehringer Ingelheim International GmbH or one or more of its affiliated companies

FLOW CHART TREATMENT B

Day	Planned time [h:min]	Approx. time [h:min]	Event and comment	Drug administration	Laboratory ¹	UVB/UVA irradiation	Photosensitivity assessment	Physical Exam	12-lead ECG ⁴	Vital signs 4	AE/Concomitant Mediation
-28 to -3			Screening		X			X	X	X	X
-3						X^4	X^6				X
-2						X^7	X^5				X
-1			Admission		X	X^8	X^5	X	X	X	X
1	0:00	8:00	Randomization				X^7				X
2	24:00	8:00									X
3	48:00	8:00		X							X
		20:00		X							
4	72:00	8:00		X							X
		20:00		X							
5	96:00	8:00		X							X
		20:00		X							
6	120:00	8:00		X							X
		20:00		X							
7	144:00	8:00		X							X
		20:00		X							
8	168:00	8:00		X	X						X
	170:00	10:00				X					
	170:10	10:10					X				
	171:00	11:00					X				
9	192:00	8:00									X
	194:00	10:00					X				
10	216:00	8:00									X
	218:00	10:00					X				
11	240:00	8:00						X	X	X	X
	242:00	10:00	Discharge				X				
15			EOT ²		X			X	X	X	X

Boehringer Ingelheim

BI Trial No.: 1407-0037

c27983101-03 Clinical Trial Protocol Page 9 of 79

Proprietary confidential information © 2020 Boehringer Ingelheim International GmbH or one or more of its affiliated companies

For the laboratory tests performed at each particular visit refer to the Tables: 5.2.3:1 and 5.2.3:2 for Photosensitivity assessments refer to the section 5.1.

- 2 Patients who discontinue trial treatment prematurely-should undergo the End of Treatment (EOT) visit 7 days thereafter.
- 3 Measurements of vital signs (BP; PR; BT) and ECG should precede blood sampling

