8.3.1 Source documents

In accordance with regulatory requirements, the investigator should prepare and maintain adequate and accurate source documents and trial records that include all observations and other data pertinent to the investigation on each trial patient. Source data as well as reported data should follow the "ALCOA principles" and be attributable, legible, contemporaneous, original and accurate. Changes to the data should be traceable (audit trail).

Data reported on the CRF must be consistent with the source data or the discrepancies must be explained.

Before providing any copy of subjects' source documents to the sponsor, the investigator must ensure that all patient identifiers (e.g. patient's name, initials, address, phone number, social security number) have properly been removed or redacted from any copy of the subjects' source documents.

If the subject is not compliant with the protocol, any corrective action e.g. re-training must be documented in the subject file.

For the CRF, data must be derived from source documents, for example:

- Subject identification: gender, year of birth (in accordance with local laws and regulations)
- Subject participation in the trial (substance, trial number, patient number, date patient was informed)
- Dates of Subject's visits, including dispensing of trial medication
- Medical history (including trial indication and concomitant diseases, if applicable)

c27983101-03 Clinical Trial Protocol Page 70 of 79

Proprietary confidential information © 2020 Boehringer Ingelheim International GmbH or one or more of its affiliated companies

- Medication history
- Adverse events and outcome events (onset date (mandatory), and end date (if available))
- Serious adverse events (onset date (mandatory), and end date (if available))
- Concomitant therapy (start date, changes)
- Originals or copies of laboratory results and other imaging or testing results, with proper documented medical evaluation (in validated electronic format, if available)
- Completion of Subject's participation in the trial" (end date; in case of premature discontinuation document the reason for it).

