Subjects will receive 500 mg ciprofloxacin starting on the morning of Day 3. Twelve (12) hours later, subjects received their second dose of 500 mg ciprofloxacin. Subjects continued a twice-daily dosing regimen through to the morning of Day 8 to ensure they reached pharmacokinetic steady state. Photosensitivity assessments will occur at baseline and following the last dose of ciprofloxacin.

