17.1. ADVERSE EVENTS

An AE is defined as any untoward medical occurrence in a patient or clinical investigation subject administered a medicinal product and which does not necessarily have to have a causal relationship with this treatment. An AE can therefore be any unfavorable and unintended sign (including an abnormal laboratory finding), symptom, or disease temporally associated with the use of a medicinal product, whether or not considered related to the medicinal product.

Protocol-specified Adverse Events of Special Interest (AESI) and infection AEs are identified on the eCRF by the investigator.

All adverse events with an onset between start of study medication and 7 days after the last dose study medication (i.e., end of the residual effect period [REP]) will be assigned to the on-treatment period for evaluation and considered as on-treatment AEs. Only on treatment AEs are considered for the summary of adverse events. Adverse Events (AEs) will be coded using MedDRA.

Treatment-emergent adverse events (TEAEs) are defined as AEs occurring between start of study medication and 7 days after the last dose study medication (i.e., end of the REP) inclusive. Adverse events that start before first study medication intake and deteriorate under treatment will also be considered as 'treatment-emergent'.

Pretreatment AEs are defined as AEs occurring prior to dosing. These events will be presented in the listings only and are not included in the tabular summary of AEs.

See APPENDIX 2 for handling of partial dates for AEs. In the rare case where it is not possible to assess treatment emergence, the AE will be classified as treatment emergent (i.e. the worst case).

Intensity (Severity)

The AE intensity is classified as mild/moderate/severe. TEAEs starting after the first dose of study medication with a missing severity will be classified as severe for analysis purposes. If a subject reports a TEAE more than once within that system organ class (SOC)/preferred term (PT), the AE with the worst case severity will be used in the corresponding severity summaries.

Causal Relationship to Study Medication

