APPENDIX 2. PARTIAL DATE CONVENTIONS

Imputed dates will NOT be presented in the listings.

ALGORITHM FOR TREATMENT EMERGENCE OF ADVERSE EVENTS:

START DATE	STOP DATE	ACTION
Known	Known	If start date < study med start date, then not TEAE If start date >= study med start date, then TEAE
	Partial	If start date < study med start date, then not TEAE If start date >= study med start date, then TEAE
	Missing	If start date < study med start date, then not TEAE If start date >= study med start date, then TEAE
Partial, but known components show that it cannot be on or after study med start date	Known	Not TEAE
	Partial	Not TEAE
	Missing	Not TEAE
Partial, could be on or after study med start date	Known	If stop date < study med start date, then not TEAE If stop date >= study med start date, then TEAE
	Partial	Impute stop date as latest possible date (i.e. last day of month if day unknown or 31st December if day and month are unknown), then: If stop date < study med start date, then not TEAE If stop date >= study med start date, then TEAE
	Missing	Assumed TEAE

Document: L:\BIOS\Boehringer_Ingelheim_Pharmaceuticals\BI730357\1407-0037_MZA56588\Biostatistics\Documentation\SAP

Author: [REDACTED]

Version Number:

Final V2.0

Version Date:

23JUL2020

Template No: CS_TP_BS016 – Revision 5
Effective Date: 01Apr2018

Reference: CS_WI_BS005

START DATE	STOP DATE	ACTION
Missing	Known	If stop date < study med start date, then not TEAE If stop date >= study med start date, then TEAE
	Partial	Impute stop date as latest possible date (i.e. last day of month if day unknown or 31st December if day and month are unknown), then: If stop date < study med start date, then not TEAE If stop date >= study med start date, then TEAE
	Missing	Assumed TEAE

ALGORITHM FOR PRIOR / CONCOMITANT MEDICATIONS:

START DATE	STOP DATE	ACTION
Known	Known	If stop date < study med start date, assign as prior If stop date >= study med start date and start date <= end of treatment, assign as concomitant If stop date >= study med start date and start date > end of treatment, assign as post study
	Partial	Impute stop date as latest possible date (i.e. last day of month if day unknown or 31 st December if day and month are unknown), then: If stop date < study med start date, assign as prior If stop date >= study med start date and start date <= end of treatment, assign as concomitant If stop date >= study med start date and start date > end of treatment, assign as post treatment

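### SAP Appendix 2 counts an AE that starts before the first dose, but on the same calendar date, as treatment-emergent, while SAP 17.1 calls it pre-treatment

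*SAP*

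**What the plan says.** SAP 17.1 (Adverse Events) sets the boundary at the dose itself: "Pretreatment AEs are defined as AEs occurring prior to dosing". Those events go to the listings and stay out of the summary tables. Treatment-emergent events run from the start of study medication to 7 days after the last dose. A carry-over rule is added: "Adverse events that start before first study medication intake and deteriorate under treatment will also be considered as 'treatment-emergent". For missing detail the section refers the reader on: "See APPENDIX 2 for handling of partial dates for AEs". Where emergence cannot be assessed, the event is classed as treatment-emergent.

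SAP Appendix 2 carries the partial-date title but also contains rows for fully known start dates. All three of these rows (stop date known, partial or missing) give the same pair of instructions: "If start date < study med start date, then not TEAE" and "If start date >= study med start date, then TEAE". Neither uses a time of day.

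On timing, both Part A flow charts in the protocol mark an AE check at -1:00 (about 07:00) on Day 1 and the first dose at 0:00 (about 08:00). For Part B, SAP 3.1 states: "Subjects will receive 500 mg ciprofloxacin starting on the morning of Day 3". On data capture, protocol 8.3.1 lists "Adverse events and outcome events (onset date (mandatory), and end date (if available" and mentions no onset time.

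**The concern.** A programmer who follows Appendix 2 literally will tabulate as treatment-emergent an event that began before any drug was taken, although the SAP's own definition sends it to the listings. A programmer who follows 17.1 will do the opposite. The SAP does not say which text governs a fully known date that equals the first-dose date.

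At stake are the treatment-emergent AE tables, where groups are small enough for one subject to be visible. There is also a knock-on: SAP 17.1 regards a treatment-emergent event with missing causality as related, so a pre-dose event with that field blank could appear as drug-related.

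**Working it through.** There is no planned figure to reproduce. The check applies the two rules to the same events and then sizes one misclassified subject.

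**Inputs**
- First dose: Day 1, about 08:00, in Part A (both flow charts); Day 3, about 08:00, in Part B (Part B flow chart). Days follow flow-chart numbering.
- Appendix 2, known start date: treatment-emergent if onset date ≥ first-dose date.
- SAP 17.1: pre-treatment if onset precedes dosing, otherwise treatment-emergent. Worsening is set aside here.
- Group sizes: 27 active and 9 placebo in each Part A dose group, and 12 on ciprofloxacin (protocol 3.2). SAP 17 pools placebo across dose groups for safety: 9 + 9 = 18.

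**Step 1: apply both rules to illustrative onsets**

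| Onset | BI 730357/placebo, Appendix 2 | BI 730357/placebo, 17.1 | Ciprofloxacin, Appendix 2 | Ciprofloxacin, 17.1 |
|---|---|---|---|---|
| Day -1, 20:00 | not TEAE | pre-treatment | not TEAE | pre-treatment |
| Day 1, 07:00 | **TEAE** | **pre-treatment** | not TEAE | pre-treatment |
| Day 1, 09:00 | TEAE | TEAE | not TEAE | pre-treatment |
| Day 2, 12:00 | TEAE | TEAE | not TEAE | pre-treatment |
| Day 3, 07:00 | TEAE | TEAE | **TEAE** | **pre-treatment** |
| Day 3, 09:00 | TEAE | TEAE | TEAE | TEAE |

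The rules disagree in two cells: Part A on Day 1 before the dose, and Part B on Day 3 before the dose. The affected onset window in each part runs from midnight to about 08:00 on the first-dose date. The Day 1 09:00 and Day 2 rows differ between parts under either rule, because ciprofloxacin starts two days later. That is a design feature and not a result of the conflict.

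**Step 2: see whether another SAP rule settles it**
- SAP 6.5 treats a measurement coinciding with study drug as pre-dose, but excludes AEs.
- The worst-case default in 17.1 is for events whose emergence cannot be assessed. An event recorded at the -1:00 check can be assessed.
- Appendix 2 has no row for a pre-dose event that worsens, so the known-date rows also omit the carry-over rule of 17.1.

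**Step 3: size per misclassified subject** (100 × 1/n)
- BI 730357 dose group: 100 × 1/27 = 3.7 points
- Placebo Pooled: 100 × 1/18 = 5.6 points
- Ciprofloxacin: 100 × 1/12 = 8.3 points

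The non-serious TEAE table includes preferred terms above 5% in at least one group. One subject in Placebo Pooled or on ciprofloxacin passes that threshold; one in a BI 730357 dose group does not.

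**The case against.** The strongest reply is that 17.1 already contains the right rule. It confines pre-dose events to listings and cites Appendix 2 only for partial dates, so the appendix need not override it. This stands as a reading, and it is why the point is a conflict to reconcile. It does not remove the conflict, because the appendix gives explicit instructions for fully known dates.

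Second, counting same-day events as treatment-emergent is a cautious convention when only a date is held, and only the onset date is stated as mandatory. This also stands, and the fix keeps that default where the order is unknown. It does not justify the default for an event already on record before the dose.

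Third, the 5% threshold is crossed by any single event in a group of 18 or 12, however emergence is defined. True: this reflects group size and adds no weight to the point.

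A reader might infer something stronger: that reactions to the baseline UV test will be charged to BI 730357 and placebo but never to the positive control, which would distort the photosafety comparison. The protocol does say "Baseline irradiation for Irradiation Condition 3 will occur on Day -1 with baseline inflammatory responses assessed at" 10 minutes and 1 hour that day, with a 24-hour reading on Day 1. The documents still do not support the inference, for four reasons:
- Test-site reactions are scored on their own scales (protocol 5.1), and nothing says that they are also recorded as AEs.
- Appendix 2 uses the start date, not the date of the reading. A reaction first seen at 10 minutes or 1 hour has a Day -1 onset and is already not treatment-emergent.
- The date-only rule also catches ciprofloxacin events on Day 3 before dosing.
- Most of the difference between the parts comes from the Day 3 start and would remain after the fix.

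**Conclusion.** The point holds as a minor inconsistency. As written, the known-date rows of Appendix 2 give a result that SAP 17.1 calls wrong for any event starting on the first-dose date before the dose. The Part A schedule includes an AE check where such an event can be recorded.

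The effect is 3.7, 5.6 or 8.3 percentage points per affected subject, depending on the group. These figures assume the planned group sizes and that Appendix 2 is programmed literally. The documents give no frequency for such events, so no expected count is offered.

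The consequence is limited to over-counting in descriptive tables; no safety hypothesis testing is planned. BI 730357 and placebo share the rule and the schedule within each dose group, so their contrast is not biased in direction. The primary analysis of the photosensitivity index is unaffected.

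**What to change.** Align Appendix 2 with SAP 17.1 for events whose start date equals the first-dose date:

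1. Compare onset date and time with first-dose date and time. Earlier is pre-treatment; at or after is treatment-emergent.
2. If no onset time is held, treat an event recorded at the scheduled pre-dose assessment as pre-treatment.
3. Keep the worsening rule of 17.1 and add a row for it in Appendix 2.
4. Default to treatment-emergent only if the order relative to dosing cannot be determined.

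The cost is a short SAP edit and a few lines of programming. The data need is an onset time or a visit label for first-dose-day events. In Part B the Day 3 AE mark shares the 08:00 row with the dose, so the visit label alone may not settle the order there; without an onset time, such events fall to the default. The downside is that a few events may move from the treatment-emergent tables to the listing, where they stay visible.

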APPENDIX 3. LABORATORY TESTS

Functional lab group	Test name	A ¹	B ²	C ³
Haematology	Haematocrit	X	X	X
	Haemoglobin	X	X	X
	Red blood cells (RBC)	X	X	X
	White blood cells (WBC)	X	X	X
	Platelet count	X	X	X
	MCV	X	X	X
	MCH			
	MCHC			
	RDW			
Automatic WBC differential (relative and absolute)	Neutrophiles total	X	X	X
	Lymphocytes total	X	X	X
	Eosinophiles	X	X	X
	Basophiles	X	X	X
	Monocytes	X	X	X
	Lymphocytes			
Manual differential WBC (if automatic differential WBC is abnormal)	Polymorphnuclear neutrophils (segs), band neutrophils (stabs), eosinophils, basophils, monocytes, lymphocytes			
Coagulation	Activated partial thromboplastin time (aPTT)	X		
	Prothrombin Time (PT)	X		
	INR	X		
Functional lab group	Test name			
Enzymes	Aspartate aminotransferase (AST)	X	X	X
	Alanine aminotransferase (ALT)	X	X	X
	Alkaline phosphatase (AP)	X	X	X
	Gammaglutamyl transferase (GGT)	X	X	X
	Creatine kinase (CK)	X		
	Lipase	X		X
	Amylase	X		X

Document: L:\BIOS\Boehringer_Ingelheim_Pharmaceuticals\BI730357\1407-0037_MZA56588\Biostatistics\Documentation\SAP

Author: [REDACTED]

Version Number:

Final V2.0

Version Date:

23JUL2020

Template No: CS_TP_BS016 – Revision 5
Effective Date: 01Apr2018

Reference: CS_WI_BS005

Substrates	Glucose Creatinine Urea Nitrogen Uric Acid Total bilirubin Direct bilirubin Total protein Albumin Globulin Albumin/Globulin ratio C-Reactive Protein (CRP) Total cholesterol	X X X X X X X X X X X	X X X X X X	X X X X
Electrolytes	Calcium Sodium Potassium Chloride Phosphate	X X X X X		X X X X
Serum Pregnancy test (only for female subjects of childbearing potential) at screening, day -1 and if urine pregnancy test is positive	Human Serum Chorionic Gonadotropin	X	X ⁴	
Urinalysis (Stix)	Urine nitrite Urine protein Urine glucose Urine ketone Urine bilirubin Urine Blood Urine leukocyte esterase Urine pH Specific gravity	X X X X X X X X		X X X X
Urine sediment (microscopic examination if erythrocytes, leukocytes nitrite or protein are abnormal in urine)	Only positive findings will be reported (e.g. presence of sediment bacteria, casts in sediment, squamous epithelial cells, erythrocytes, leukocytes)			

Document: L:\BIOS\Boehringer_Ingelheim_Pharmaceuticals\BI730357\1407-0037_MZA56588\Biostatistics\Documentation\SAP

Author: [REDACTED]

Version Number:

Final V2.0

Version Date:

23JUL2020

Template No: CS_TP_BS016 – Revision 5
Effective Date: 01Apr2018

Reference: CS_WI_BS005

Urine Pregnancy test (only for female subjects of childbearing potential) at EoT	Human Chorionic Gonadotropin in the urine			X
---	---	--	--	---

¹ A: parameters to be determined at screening examination

² B: parameters to be determined on Days 1 and 8

³ C: parameters to be determined at end of trial examination

⁴ Day -1 only

Document: L:\BIOS\Boehringer_Ingelheim_Pharmaceuticals\BI730357\1407-0037_MZA56588\Biostatistics\Documentation\SAP

Author: [REDACTED]

Version Number:

Final V2.0

Version Date:

23JUL2020

Template No: CS_TP_BS016 – Revision 5
Effective Date: 01Apr2018

Reference: CS_WI_BS005
